## 4.0 TREATMENT PLAN

## 4.1 Study Design

The study will consist of two phases-

4.1.1 Phase I dose-escalation Phase for relapsed or refractory B-cell ALL or CML in lymphoid blast phase patients will start therapy with bosutinib at 300 mg orally once daily (which is 40% lower than the FDA approved dose of 500 mg orally once daily). Bosutinib will be dose-escalated in subsequent cohorts in a standard 3+3 study design. Patients will receive inotuzumab ozogamicin as an intravenous infusion over approximately one hour on a weekly schedule (0.8 mg/m^2 IV day 1, 0.5 mg/m^2 day 8 (±3 days), and 0.5 mg/m^2 day 15 (±3 days). A minimum of 6 days should be maintained between subsequent doses.

A cycle is defined as 28 days, however, start of cycle 2 may be delayed if the patient achieves a CR or CRi and/or to allow toxicity recovery.

Dose Level	Bosutinib (mg/day)	Inotuzumab ozogamicin IV (mg/m  ),
	orally once daily	repeat cycles every 3-4 weeks
-1	200	Day 1 - 0.8 mg/m 
		Day 8 - 0.5 mg/m 
		Day 15 - 0.5 mg/m 
1 (starting dose)	300	Day 1 - 0.8 mg/m 
		Day 8 - 0.5 mg/m 
		Day 15 - 0.5 mg/m 
2	400	Day 1 - 0.8 mg/m 
		Day 8 - 0.5 mg/m 
		Day 15 - 0.5 mg/m 
3	500	Day 1 - 0.8 mg/m 
		Day 8 - 0.5 mg/m 
		Day 15 - 0.5 mg/m 

**4.1.1.1** For Cycles 2 to 6, if there are no peripheral blood blasts, the inotuzumab ozogamicin dose is reduced to 1.5 mg/m^2 total but continues on a weekly

schedule (0.5 mg/m^2 days 1, 8 ( $\pm$ 3 days) and 15 ( $\pm$ 3 days). The rationale for this is that, based on prior experience at our institution, the number of circulating blast cells is a significant covariant affecting inotuzumab clearance and therefore, once the peripheral blood blasts clear, the dose may be reduced maintaining efficacy. This will also reduce the risk of toxicity for subsequent cycles.

- **4.1.1.2** A minimum of 6 days should be maintained between the doses.
- 4.1.1.3 For patients who have achieved CR/CRi the next cycle (cycle 2 and onwards) will begin when ANC ≥1.0, and platelet count ≥75. These count recovery guidelines could be modified based on treating physician assessment if determined to be in the best interest of the patient after discussion with study PI (e.g., if there is evidence of minimal residual disease).
- **4.1.1.4 Transition to the every 4-weekly schedule** In order to decrease the toxicity of the subsequent cycles, once a response is confirmed (CR, CRi, or whenever CCyR and/or absence of MRD by flow cytometry is documented), subsequent cycles will be administered at a dose of 1.0 mg/m^2 once every 4 weeks. Note: Patients who have been switched to every 4 weeks schedule may return to the weekly schedule if there is concern about recurrence of the disease.
- **4.1.1.5** Patients who experience a clinical benefit (CR/CRi/PR) with acceptable toxicity can receive up to a total of 6 cycles of inotuzumab ozogamicin. Treatment with bosutinib should continue indefinitely as long as patient is tolerating it well and responding to it.
- **4.1.1.6** Bosutinib will be dose-escalated in subsequent cohorts in a standard 3+3 study design (see Section 11.2).

# 4.1.1.7 Dosing for the Frontline Ph+ ALL or CML-LBC Cohort

**Phase I dose-escalation Phase:** in the phase I portion of the study, frontline Ph+ ALL or CML-LBC patients will start therapy with bosutinib at 300 mg orally once daily. This dose has already been shown to be safe in the relapsed cohort (we have treated 3 patients with R/R ALL, and no DLT was noted at the 300mg dose level). Bosutinib will be dose-escalated in subsequent cohorts in a standard 3+3 study design.

Patients will receive inotuzumab ozogamicin as an intravenous infusion over approximately one hour on a weekly schedule ( $0.8 \text{ mg/m}^2$  IV day 1,  $0.5 \text{ mg/m}^2$  day 8 (±3 days), and 0.5 mg/m^2 day 15 (±3 days). A minimum of 6 days should be maintained between subsequent doses.

A cycle is defined as 28 days, however, start of cycle 2 may be delayed if the patient achieves a CR or CRi and/or to allow toxicity recovery.

Dose Level	Bosutinib (mg/day)	Inotuzumab ozogamicin IV (mg/m  ),
	orally once daily	repeat cycles every 3-4 weeks
-1	200	Day 1 - 0.8 mg/m 
		Day 8 - 0.5 mg/m 
		Day 15 - 0.5 mg/m 
1 (starting dose)	300	Day 1 - 0.8 mg/m 
		Day 8 - 0.5 mg/m 
		Day 15 - 0.5 mg/m 
2	400	Day 1 - 0.8 mg/m 
		Day 8 - 0.5 mg/m 
		Day 15 - 0.5 mg/m 
3	500	Day 1 - 0.8 mg/m 
		Day 8 - 0.5 mg/m 
		Day 15 - 0.5 mg/m 

For Cycles 2 to 6, if there are no peripheral blood blasts, the inotuzumab ozogamicin dose is reduced to  $1.5 \text{ mg/m}^2$  total but continues on a weekly schedule ( $0.5 \text{ mg/m}^2$  days 1, 8 (±3 days) and 15 (±3 days). A minimum of 6 days should be maintained between the doses. For patients who have achieved CR/CRi – the next cycle (cycle 2 and onwards) will begin when ANC ≥1.0, and platelet count ≥75. These count recovery guidelines could be modified based on treating physician assessment if determined to be in the best interest of the patient after discussion with study PI (e.g., if there is evidence of minimal residual disease).

**Transition to the every 4-weekly schedule** – In order to decrease the toxicity of the subsequent cycles, once a response is confirmed (CR, CRi, or whenever CCyR and/or absence of MRD by flow cytometry is documented), subsequent cycles will be administered at a dose of 1.0 mg/m^2 once every 4 weeks. Note: Patients who have been switched to every 4 weeks schedule may return to the weekly schedule if there is concern about recurrence of the disease.

Patients who experience a clinical benefit (CR/CRi/PR) with acceptable toxicity can receive up to a total of 6 cycles of inotuzumab ozogamicin. Treatment with bosutinib should continue indefinitely as long as patient is tolerating it well and responding to it.

NOTE: For all patients included in this trial, inotuzumab doses may be omitted if deemed in the best interest of the patient (for e.g. patients with plans of undergoing stem cell transplant) by the treating physician (after discussion with the study PI). The reason for omission will be noted in the medical record. Patients who achieve MRD negative remission may have further doses of inotuzumab omitted, if deemed in the best interest of the patient by the treating physician (in discussion with the study PI).

## 4.1.2 Evaluation of dose limiting toxicity (DLT)

- **4.1.2.1** Prior to advancing/changing cohorts a cohort summary will be completed and submitted to the Medical Monitor in the IND Office.
- **4.1.2.2** DLT is defined as clinically significant non-hematologic adverse event or abnormal laboratory value assessed as unrelated to disease progression, intercurrent illness, or concomitant medications and occurring during the first cycle of therapy that meets any of the following criteria:
  - CTCAE Grade 3 or 4 AST (SGOT) or ALT (SGPT) for  $\geq$  14 days
  - All other clinically significant non-hematological adverse event possibly related to study drugs that is Grade 3 or 4 according to the NCI common terminology criteria version 4.0. with the following exceptions:
    - Grade 3 or 4 nausea, vomiting and diarrhea will be considered DLT only if not controlled by optimal therapy.
    - Grade 3 biochemical abnormalities (e.g., lipase or bilirubin elevation) will only be considered DLT if accompanied by clinical consequences. Grade 3 or 4 electrolyte abnormalities will only be considered DLT if possibly related to study drug and not corrected by optimal replacement therapy.
  - Hematologic DLT is defined as absolute neutrophil count (ANC) <0.5  $\times 10^{9}$ /L or platelet count <25  $\times 10^{9}$ /L with a hypocellular bone marrow lasting for 6 weeks or more after the start of a course in the absence of residual leukemia (i.e., with less than 5% blasts). (In case of a normocellular bone marrow with <5% blasts, 8 weeks with pancytopenia will be considered DLT). Anemia will not be considered for the definition of DLT.
  - The last patient enrolled in each cohort will be observed for toxicity for 28 days (1 cycle) prior to advancing to the next dose level.
- **4.1.2.3** Patients that are removed from study during cycle 1 for any reason other than toxicity and have not experienced DLT will be replaced.
- **4.1.2.4** For the purpose of defining DLT, the first cycle will be considered; however information on observed toxicities during subsequent cycles will be collected from all patients.

- **4.1.3** Cycle 1 is a 4 week cycle. However, cycle 2 may be started up to 1 week early if the patient has not achieved a CR or CRi and/or has persistent disease or rapidly proliferating disease, provided all drug-related toxicity has recovered to grade 1 or less. All subsequent cycles are 4 week cycles. Note: Subsequent cycles may start early if there is recovery of all toxicity related to the study drugs to grade 1 or less, but not earlier than day 21.
  - **4.1.3.1** Subsequent cycles may be delayed for recovery of toxicity. Delays in start of subsequent cycles greater than 8 weeks should be discussed with the principal investigator.
  - **4.1.3.2** If the peripheral counts do not recover (ANC <1  $x10^{9}/L$  and/or platelets <75  $x10^{9}/L$ ) but there is evidence of residual leukemia in the bone marrow, subsequent cycles can be administered at the discretion of the treating physician.
- **4.1.4** **Phase II Phase:** Once the MTD (or bosutinib 500 mg dose level, if MTD not exceeded at this level) is established in each cohort separately, a phase II portion will commence respectively for each cohort. For each cohort, the 6 patients at MTD from the phase I dose part will be enrolled in the phase II portion of the study.

Patients will receive bosutinib per the MTD established in the Phase I study. Patients will receive inotuzumab ozogamicin at the same dose and schedule as for the Phase I part of the study. For each cohort, a maximum of 28 patients (including the 6 patients at MTD from the phase I dose part) will be enrolled in the phase II portion of the study.

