# Phase I

Bosutinib will be dose-escalated in a standard 3+3 study design separately for two cohorts (relapsed ph+ALL and newly diagnosed Ph+ ALL or CML-LBC with age  $\geq$ 60). Patients will be entered sequentially to each dose level. Three combination dose levels are defined. The starting dose is dose 1. If none of the first 3 patients at a dose level experience first cycle dose-limiting toxicity (DLT), new patients may be entered at the next higher dose level. If 1 of 3 patients experience first cycle DLT, up to 3 more patients are started at that same dose level. If 1 of 6 experience DLT, then new patients may be entered at the next higher dose level. If 2 or more

experience first cycle DLT, no further patients are started at that dose. The MTD is the highest dose level in which <2 patients of 6 develop first cycle DLT. Detailed dose escalation rules are described in the following section. A maximum of 18 patients will enroll in the phase I study. DLT definition is provided in Section 4.1.2.

Number of Patients with	Decision	
DLT at a Dose Level		
0 of 3	Escalate and evaluate in 3 subsequent patients.	
1 of 3	Enroll 3 additional subjects at this dose level.	
	The MTD has been exceeded. Dose escalation will stop and this	
	level will be declared the maximum administered dose. Evaluate	
>/=2 of 3	3 additional patients at the prior dose level if only three were	
-1-2 81 3	treated at that dose previously.	
	An interim dose may be explored if the increments between	
	maximally administered dose and the next lower dose is $>50\%$ .	
1 of 6	Escalate dose and evaluate in 3 subsequent patients.	
=1 out of 6 at the Highest</td 	Dose Below the Maximum	This is the MTD.	
Administered Dose		
	The MTD has been exceeded. Dose escalation will stop and this	
	level will be declared the maximum administered dose. Evaluate	
>/=2  of  6	3 additional patients at the prior dose level if only three were	
>/-2 81 8	treated at that dose previously.	
	An interim dose may be explored if the increments between	
	maximally administered dose and the next lower dose is $>50\%$ .	

Table 11.1 Dose-Escalation Decision Rules for 3+3 Escalation Schema is provided below:

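### The next dose level may open after the last patient's 28 days, but hematologic DLT takes 6 or 8 weeks to establish and no rule holds escalation for unresolved cytopenia

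*Combined protocol and SAP*

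**What the plan says.** Hematologic DLT (Section 4.1.2.2) is ANC below 0.5 or platelets below 25 x10^9/L "with a hypocellular bone marrow lasting for 6 weeks or more after the start of a course in the absence of residual leukemia". With a normocellular marrow and under 5% blasts, "8 weeks with pancytopenia will be considered DLT".

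The same list says the last patient in each cohort "will be observed for toxicity for 28 days (1 cycle) prior to advancing to the next dose level".

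Section 4.1.2.4 adds: "For the purpose of defining DLT, the first cycle will be considered". Section 4.1.3 says "Cycle 1 is a 4 week cycle", while Section 4.1.1 notes that "start of cycle 2 may be delayed if the patient achieves a CR or CRi and/or to allow toxicity recovery".

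Under Section 11.2 (Phase I), after 0 of 3 or 1 of 6 DLTs, "new patients may be entered at the next higher dose level". The end point of escalation is defined thus: "The MTD is the highest dose level in which <2 patients of 6 develop first cycle DLT". Table 11.1 has rows for observed DLT counts and none for a patient whose DLT status is still open.

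Before any advance, a cohort summary goes to the Medical Monitor (Section 4.1.2.1). No criterion for waiting is attached to it.

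**The concern.** A 3+3 decision should rest on a DLT count that is complete for every toxicity on the list. Here one listed toxicity cannot be complete on the earliest decision day. A patient with platelets of 15 and a clear, hypocellular marrow at day 28 counts as having no DLT, although the same patient may become a DLT two weeks later.

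Low counts at day 28 are foreseeable. Section 6.3 describes cytopenias as common in this population. Section 2.0 reports Grade 3/4 neutropenia in 46% and thrombocytopenia in 65% on bosutinib 500 mg alone, for any causality and with no duration given. Under Section 6.1, the day 8 and day 15 doses need not wait for low counts.

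At stake is exposure of up to three patients to the next dose when the completed count would have required expansion to six (1 of 3) or stopping (2 or more of 6). Section 11.2 has no day-28 cut-off, so a late DLT can still be added afterwards, but the higher dose may already have been given.

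It is also unclear whether a late event counts at all. A clock that runs from the start of a course implies that a week-6 event does count. Read strictly, limiting DLT to a first cycle of four weeks would leave the hematologic criterion with nothing to capture.

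**Working it through.** **Timing (all inputs from Section 4.1.2.2)**

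- Hypocellular marrow: 6 x 7 = 42 days; 42 - 28 = 14 days short.
- Normocellular marrow: 8 x 7 = 56 days; 56 - 28 = 28 days short.
- A cohort-mate enrolled d days before the last patient is at day 28 + d on the decision day. Day 42 needs d of at least 14, and day 56 needs d of at least 28.

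The gap is certain for the last patient and applies to anyone enrolled close to that patient. Grade 3/4 AST/ALT lasting 14 days or more has a smaller version of it, when onset is after about day 14.

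**Provisions that might close the gap**

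- Delays for count or toxicity recovery (Sections 4.1.1.3, 4.1.3.1 and 6.1) govern that patient's next cycle, not the opening of the next dose level.
- Replacement (Section 4.1.2.3) covers only patients removed in cycle 1 for reasons other than toxicity.
- Reading a delayed cycle 2 as a longer cycle 1 may let a late event count, but the required wait is still 28 days.

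None of them holds escalation.

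**Size (illustrative; the plan gives no figure to reproduce and no rate for prolonged cytopenia)**

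Assume independent patients, a non-hematologic DLT probability nh = 0.15 that is always seen in time, and a hematologic DLT probability h. Then p = 1 - (1 - nh)(1 - h) and q = 1 - p.

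- All DLTs seen: P(escalate) = q^3 + 3pq^2 x q^3.
- Last patient of each trio unseen for hematologic DLT: A = q^2(1 - nh) is the chance of 0 of 3 seen, B = 2pq(1 - nh) + q^2 x nh is the chance of 1 of 3 seen, and P(escalate) = A + B x A.

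At h = 0.15: p = 0.2775, A = 0.4437, B = 0.4191, so P = 0.4437 + 0.4191 x 0.4437 = 0.630, against 0.541 with all seen.

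A step that the completed count would not have allowed arises in two ways: 0 of 3 seen with one pending, which is q^2(1 - nh)h; or 1 of 3 seen, then at most 1 of 6 seen but 2 or more in truth, obtained by enumerating both trios. At h = 0.15 these are 0.0666 + 0.0472 = 0.114.

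| h | P(escalate), all seen | Last of each trio unseen | First trio known by the six-patient decision | Step not allowed, last of each trio unseen | Step not allowed, first trio known |
|---|---|---|---|---|---|
| 0.02 | 0.779 | 0.791 | 0.788 | 0.019 | 0.016 |
| 0.05 | 0.725 | 0.755 | 0.748 | 0.045 | 0.037 |
| 0.10 | 0.632 | 0.693 | 0.678 | 0.083 | 0.068 |
| 0.15 | 0.541 | 0.630 | 0.607 | 0.114 | 0.091 |

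If all patients enroll together and no hematologic DLT is visible, P(escalate) is 0.814 whatever h is.

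**The case against.** The strongest reply is that the event is pending but not hidden. A patient heading for a week-6 DLT has visibly low counts at day 28. Counts are taken 1 to 3 times weekly in cycle 1, a marrow is due before cycle 2, the Medical Monitor sees a summary, 28 days is a minimum, and entry at the next level is permitted rather than required. The probabilities assume that nobody acts on any of this, so at each assumed rate they are an upper bound on the practical effect. That point stands. Still, a sensible team might wait, and the rule should not depend on it.

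The size can also be stated lower. At h = 0.15, 0.0666 of the 0.114 is a case where the completed count only calls for expansion, and in 0.025 of it the expanded cohort would have escalated anyway. The net rise in P(escalate) is 0.066 to 0.089 at 15%, 0.023 to 0.030 at 5%, and 0.009 to 0.012 at 2%.

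The documents do not support the upper rates. Hematologic DLT requires a marrow clear of leukemia. With the single-agent response of 57%, or 3 of 7 in Ph+ ALL (Section 2.0), 15% of all patients would mean 0.15/0.57 = 26% to 0.15/0.43 = 35% of responders. The Section 2.0 cytopenia rates cover any duration and include patients with active disease. These points also stand, and they limit the size.

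Finally, there are backstops. The MTD needs six patients, phase II has continuous toxicity stopping, and bosutinib rises in 100 mg steps to its approved single-agent dose. They reduce the risk of a wrong final dose but do not prevent premature exposure to the next one.

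**Conclusion.** The concern holds and should be fixed. As written, the plan permits escalation on a count that cannot yet include one of its own listed DLTs, and no provision holds escalation for unresolved cytopenia. This follows from the day counts alone and needs no assumed rate.

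The practical size does rest on assumptions: 15% non-hematologic DLT, independence, and no action on visible low counts. The effect is small if hematologic DLT occurs in 2% to 5% of patients, and about 9 to 11 percentage points of disallowed steps at 15%, a rate the documents do not support. The case for changing the text is that it is a cheap safety correction, not that large harm is likely.

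**What to change.** In Sections 4.1.2.2 and 11.2, add a conditional hold. If any patient at the current dose level has ANC below 0.5 or platelets below 25 x10^9/L without residual leukemia on the decision day, escalation waits until counts recover or the criterion is met or ruled out. The limit is day 42 of that patient's course, or day 56 if the marrow is normocellular. A single-lineage cytopenia with a normocellular marrow cannot become the pancytopenia DLT, so it is ruled out and ends the hold; defining pancytopenia would make this clear. Apply the same hold to ongoing Grade 3/4 AST/ALT until 14 days from onset.

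In Section 4.1.2.4, state that a DLT arising from course 1 but confirmed after day 28 counts in that level's total and in the MTD test of fewer than 2 of 6.

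The cost is protocol wording and a delay of up to about 2 to 4 weeks, only in cohorts with a pending event. Because cytopenias are common here, that may be more than the occasional cohort. Some cohorts may expand from 3 to 6 more often, within the existing maximum of 18. No new scheduled procedure is needed: counts are already frequent, the end-of-cycle-1 marrow can move with a delayed cycle 2, and Section 8.0 (note 8) allows marrows as clinically indicated after CR/CRi.

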## 6.0 **DOSE MODIFICATIONS**

**6.1** Intrapatient dose reduction will be allowed depending on the type and severity of toxicity. Dose interruption may occur within a cycle until adequate recovery or omission of a dose during a given treatment cycle. While doses given within a treatment cycle (i.e., Days 8 and/or 15) need not be delayed due to neutropenia or thrombocytopenia, dose delays

within a cycle are required for drug-related non hematologic toxicity. The start of the next cycle may be delayed if additional time is required for the patient to recover from study treatment-related toxicity experienced during the current cycle. Delays in start of subsequent cycles greater than 8 weeks should be discussed with the principal investigator. Doses reduced for treatment-related toxicity should not be re-escalated without discussion with the principal investigator.

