## Non-Hematologic Bosutinib-related toxicity

Adverse Event	Action #
Grade I	Remain on current dose level
Grade II	For persistent, clinically relevant toxicity not responding to optimal management: Interrupt bosutinib, then reintroduce at the same dose or
	reduce dose by one level upon recovery to grade $\leq 1$
Grade III	For persistent, clinically relevant toxicity not responding to optimal management: Interrupt bosutinib, then dose reduce by 1 level upon recovery to grade $\leq 1$
Grade IV	Interrupt bosutinib. Discuss with PI about resuming bosutinib with appropriate dose reduction. Resumption should happen only upon recovery to grade $\leq 1$

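### Section 4.1.2.3 leaves under-exposed patients, and patients removed for toxicity short of a DLT, in the 3+3 denominator, which biases the MTD decision toward clearing a level

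*Combined protocol and SAP*

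**What the plan says.** The phase I primary endpoint is the MTD (section 11.1.1). Section 11.2 defines it as follows: "The MTD is the highest dose level in which <2 patients of 6 develop first cycle DLT". The escalation rules there and in Table 11.1 count the patients entered at a level, in threes and sixes, and do not restrict the count to evaluable patients.

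Section 4.1.2.3 states who is replaced: "Patients that are removed from study during cycle 1 for any reason other than toxicity and have not experienced DLT will be replaced". Section 4.1.2.4 fixes the window: "For the purpose of defining DLT, the first cycle will be considered". Section 4.1.2.2 leaves several toxicities outside the DLT definition. Grade 3 or 4 AST or ALT must last at least 14 days. Grade 3 biochemical abnormalities need clinical consequences. For gastrointestinal events, "Grade 3 or 4 nausea, vomiting and diarrhea will be considered DLT only if not controlled by optimal therapy". Grade 2 non-hematologic events are never DLTs.

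Other sections allow cycle 1 exposure to fall, and none excepts cycle 1:

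- The note closing section 4.1.1.7: "For all patients included in this trial, inotuzumab doses may be omitted if deemed in the best interest of the patient", after discussion with the principal investigator.
- Section 6.1: "Dose interruption may occur within a cycle until adequate recovery or omission of a dose during a given treatment cycle". It also permits dose reduction within a patient and requires within-cycle delays for drug-related non-hematologic toxicity.
- Section 6.3, for persistent, clinically relevant grade II toxicity that does not respond to optimal management: "Interrupt bosutinib, then reintroduce at the same dose or" one level lower, after recovery.
- The footnote to the section 6.3 table allows re-escalation only after at least a month free of the toxicity.

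**The concern.** A 3+3 decision is informative about a dose level only if the patients counted were exposed to that level long enough to show a DLT, or had one. Section 4.1.2.3 does not secure this, because replacement requires three conditions together: removal from study in cycle 1, a reason other than toxicity, and no DLT.

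Two groups fall outside it. The first stays on study with less than the assigned treatment. Bosutinib is the only escalated drug, so a cycle 1 bosutinib interruption or reduction matters most. The clearest case is persistent grade II toxicity, which can lead to a lower level but cannot be a non-hematologic DLT. Under the re-escalation footnote, a patient reduced in this way cannot return to the assigned level within the 28-day window. The second group is removed in cycle 1 because of a toxicity that section 4.1.2.2 does not count. The replacement rule excludes these patients by its own wording, yet they meet no DLT criterion.

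Both groups enlarge the denominator without adding to the DLT count. The resulting dose then goes forward to phase II, with up to 28 patients per cohort, 6 of them carried over from phase I.

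**Working it through.** **Plan's own figure.** Section 11.2 caps phase I at 18 patients per cohort. Three dose levels × 6 patients = 18, so the cap reproduces. It leaves no room for replacements if all three levels fill.

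**Status of each type of patient without a DLT.**

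| Cycle 1 course | Replaced under 4.1.2.3? | Counted in the 3 or 6? | Adds to the DLT count? |
|---|---|---|---|
| Leaves study for a non-toxicity reason | Yes | No | No |
| Leaves study for toxicity below the DLT definition | No | Yes | No |
| Stays on study; bosutinib interrupted or reduced for persistent grade II toxicity | No | Yes | No |
| Stays on study; inotuzumab dose omitted | No | Yes | No |

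The last two columns follow from applying sections 4.1.2.2 and 11.2 together. The text does not state them for the patients who are not replaced.

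**Size.** The relevant event is the MTD criterion, at most 1 DLT in 6. Let p be the DLT rate with full exposure, e the share of counted patients who are under-exposed, and b their DLT risk as a fraction of p. Then

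- effective rate: q = p(1 − e) + b·p·e
- chance of meeting the criterion: A(q) = (1 − q)^6 + 6q(1 − q)^5

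The documents give no values for p, e or b. All three are assumptions. The rates of 40% and 50% were chosen to lie above the 30% toxicity limit used in phase II monitoring (section 11.2).

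With no DLT risk in under-exposed patients (b = 0, the upper end):

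| p | e | q | A(q) |
|---|---|---|---|
| 0.40 | 0 | 0.400 | 0.0467 + 0.1866 = 0.233 |
| 0.40 | 0.20 | 0.320 | 0.0989 + 0.2792 = 0.378 |
| 0.40 | 1/3 | 0.267 | 0.1555 + 0.3393 = 0.495 (0.4949 before rounding) |
| 0.50 | 0 | 0.500 | 0.0156 + 0.0938 = 0.109 |
| 0.50 | 0.20 | 0.400 | 0.233 |
| 0.50 | 1/3 | 0.333 | 0.0878 + 0.2634 = 0.351 |

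With half the DLT risk in those patients (b = 0.5) and p = 0.40:

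- e = 0.20: q = 0.32 + 0.04 = 0.36, A = 0.0687 + 0.2319 = 0.301
- e = 1/3: q = 0.267 + 0.067 = 0.333, A = 0.351

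If every counted patient is adequately exposed or has had a DLT, the chances return to 23% and 11%.

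**The case against.** The strongest reply is that the text never says a patient removed for sub-DLT toxicity is scored as free of DLT. That is correct: the scoring is how the rules operate when applied together. The sponsor may intend to treat such removals as DLTs, but this is written nowhere, and the plain reading counts them in the denominator only.

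The exposure loss may also be small. The examples in the section 4.1.1.7 note are planned transplant and MRD-negative remission. The first on-treatment marrow is due at the end of cycle 1 (section 8.0), so the MRD case falls after the window. Inotuzumab is also the same at every level. This narrows the point mainly to bosutinib but does not remove it.

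There are safeguards. A cohort summary goes to the Medical Monitor before escalation, and phase II monitoring would stop with probability 0.53 at a true toxicity rate of 40% (Table 11.3). Both reduce the harm. But the summary has no stated exposure criterion, and phase II monitoring counts DLTs without an exposure requirement and acts only after the MTD has been named.

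Three stronger readings are tempting and are not supported:

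- A reader might infer that under-exposure will be common, because section 2.0 reports diarrhea in 67% of patients on single-agent bosutinib 500 mg. That figure has no grade restriction and says nothing about persistent grade II diarrhea failing optimal management in cycle 1.
- A reader might add the grade III reductions in section 6.3. Those require clinically relevant toxicity that does not respond to optimal management, and most such patients would already meet section 4.1.2.2.
- A reader might conclude that the named MTD will be a dose that few patients received. That is possible, but nothing in the documents shows it.

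**Conclusion.** The concern holds. Followed exactly, the replacement rule biases the MTD decision in one direction, toward clearing a level, because the patients it retains can enlarge the denominator without adding to the DLT count. This goes beyond missing detail, since it affects the phase I primary endpoint.

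The size cannot be read from the documents. If 20% or one third of counted patients were under-exposed with no DLT risk, a level with a true DLT rate of 40% would meet the MTD criterion with probability 38% or 49% instead of 23%. At a true rate of 50%, the figures are 23% or 35% instead of 11%. These are upper-end figures. A patient who took the assigned dose until toxicity set in has had some exposure, and at half the risk the 40% figures are 30% and 35%. With little under-exposure the bias would be small. The plan has no rule that would keep it small, and the point should be corrected.

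**What to change.** Amend section 4.1.2.3 so that escalation and MTD decisions use DLT-evaluable patients only: those with a DLT in the window, and those who completed the window with at least a stated minimum of the assigned cycle 1 treatment. The sponsor should choose that minimum, for bosutinib at the assigned level and for inotuzumab. Patients under-exposed for reasons other than drug toxicity would be replaced for the escalation decision only and kept in the safety and response sets.

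Sections 4.1.2.2, 4.1.2.3, 6.1 and 6.3 must also be reconciled, so that the protocol states how a patient removed or reduced in cycle 1 for drug toxicity below the DLT definition is counted. How the DLT definition should read is for the sponsor; this review proposes none.

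Two consequential edits follow. State the cap of 18 per cohort as evaluable patients and word the totals of 36 and 80 in section 11.2 to match. List cycle 1 dose intensity per level in the cohort summary that section 4.1.2.1 already requires.

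The cost is a short amendment and an occasional replacement patient at a level. No new procedures are needed.
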